5.2. Subject and Study Completion

Approximately 226 subjects will be screened to achieve 32 completers in treatment in Part A and 60 completers in Part B.

[figure not shown]
5.3. End of Study Definition

A subject is considered to have completed the study if he/she has completed all phases of the study, ie, Day 2 EOS for Part A and Day 29 EOS for Part B.

The end of the study (EOS) is defined as the date of the last visit for the last subject, including the follow-up telephone call.

5.4. Scientific Rationale for Study Design

Studies comparing the pharmacokinetics and safety of a drug product in Japanese and non-Japanese (eg, Caucasian) subjects allow for extrapolation of clinical data across regions. Randomization and masking minimizes bias in the assessment of safety and interpretation of results. Safety and tolerability can be clearly assessed as each subject in Part A will receive only a single dose of SJP-0132 in an ascending fashion.

6. Study Population

A sufficient number of subjects will be screened and will participate in the study. Prospective approval of protocol deviations to recruitment and enrollment criteria, also known as protocol waivers or exemptions, is not permitted.

6.1. Inclusion Criteria

Subjects are eligible to be included in the study only if all of the following criteria apply:

1. Signed the informed consent form which includes compliance with the requirements and restrictions listed in the informed consent form (ICF) and in this protocol
2. Man or woman, ≥ 18 years of age (inclusive) at the time of signing the informed consent form
3. Body mass index (BMI) within 18.5 to 30.0 kg/m^2 (inclusive) and body weight between 45 kg and 100 kg
4. Generally healthy as determined by medical history, physical examinations, clinical laboratory examination, and ophthalmologic examinations performed at Screening.
5. Have a subject reported history of Dry Eye Disease in both eyes for at least 6 months prior to Screening.
6. Dry eye symptoms at Screening and Day -1:
 - Baseline eye dryness VAS score ≥ 40 mm
 - Baseline DEQ 5 ≥ 6
7. Dry eye signs at Screening and Day -1:
 - Baseline central corneal staining (Baylor scale) of 2 to 4 in at least 1 eye (designated study eye)
8. Non-smoker or ex-smoker for > 12 months
9. If male, must agree to use contraception during the treatment period and for at least 7 days, after the last dose of study treatment and refrain from donating sperm during this period
10. If a woman of child-bearing potential (WOCBP), she must agree to use a highly effective form of contraception during the study and for 30 days after the last dose.
11. For Japanese cohort subjects, subjects must be of Japanese descent.

Note: Retesting of abnormal lab values that may lead to exclusion will be allowed once. Retesting will take place during an unscheduled visit in the screening phase.

6.2. Exclusion Criteria

Subjects are excluded from the study if any of the following criteria apply:

1. Have clinically significant systemic or ophthalmic disease
2. Have allergies to [REDACTED] or to any of the SJP-0132 ophthalmic [REDACTED] ingredients.
3. Has a positive serum pregnancy test at Screening or urine pregnancy test at Day -1.
4. Have had significant blood loss or have donated or received one or more units (450 mL) of blood or plasma within 30 days before randomization.

5. Have used or anticipates use of any prescription or over-the-counter medication, including topical medications such as ophthalmic solutions (except an ophthalmic solution specially provided by Sponsor, mydriatics, and stain used for trial examinations), nasal drops or spray, vitamins, alternative and complementary medicines (including herbal formulations) within 14 days or 5 half-lives (whichever is longer) before randomization or at any time during the study.
6. Use or anticipates use of prescribed dry eye medications (e.g. Restasis and Xiidra) within 28 days prior to randomization or at any time during the study.
7. Have used or anticipates use CYP3A4 inducers, such as St. John's Wort, within 14 days before randomization or at any time during the study.
8. Have consumed red wine, grapefruit or grapefruit juice, Seville oranges, star fruit, or any products containing these items, or any foods that may inhibit CYP3A4, within 48 hours before randomization and throughout the duration of the study
9. Have a positive urine alcohol test at Screening or Day –1
10. Have a positive urine drug test at Screening or Day –1
11. Has history of, or evidence of, alcohol or drug abuse within past 6 months prior to Screening
12. Have a positive HBsAg, HCV antibody, or HIV test at Screening
13. Have received another investigational medication within 90 days before randomization
14. Contact lens wearers who cannot discontinue the wear over the trial period (i.e., from Screening to EOS)
15. Have undergone eye surgery (including laser surgery) within the last 12 months or whom the Investigator considers unsuitable
16. Subjects whom the Investigator considers are unable or unlikely to comply with the trial protocol or scheduled Screening or Admission (e.g., planned travel outside of the trial area for a substantial portion of the trial period, scheduled hospitalization during the trial period)
17. Have a family history of sudden death
18. Have cardiac disease (e.g., cardiac arrest, ischemic cardiac disease)
19. Have abnormal serum electrolytes according to the judgment of the Investigator
20. Have a BCVA worse than 20/100 in either eye.
21. Current use of punctal plugs or anticipated insertion during study period.
22. History of permanent punctal occlusion (cautery or laser).
23. Any corneal abnormality or disease which might impact normal tear film spreading (eg: cornea scarring, keratoconus or pterygia).
24. Active or history of significant corneal disease (recurrent erosions or herpetic keratitis).
25. Known allergy or sensitivity to fluorescein, lissamine green or any of the study medications.

6.3. Lifestyle Restrictions

6.3.1. Meals and Dietary Restrictions

1. Refrain from consumption of red wine, grapefruit or grapefruit juice, Seville oranges, star fruit, or any products containing these items, or any foods that may inhibit CYP3A4, within 48 hours before randomization and throughout the duration of the study.

6.3.2. Caffeine, Alcohol, and Tobacco

1. Subjects will abstain from ingesting caffeine- or xanthine-containing products (eg, coffee, tea, cola drinks, and chocolate) for 24 hours prior to the start of dosing on Day 1 of Part A and Days 1, 2, 4, and 8 of Part B, and for the remainder of the confinement period until after collection of the final pharmacokinetic (PK). Subjects will also abstain 24 hours prior to each weekly outpatient visit.
2. Subjects will abstain from alcohol for 24 hours before the start of dosing on Day 1 of Part A and Days 1, 2, 4, and 8 of Part B until after collection of the final pharmacokinetic (PK).
3. Use of tobacco products will not be allowed from screening until after the final follow-up visit.

6.3.3. Activity

1. Subjects will abstain from strenuous exercise for 24 hours before each blood collection for clinical laboratory tests. Subjects may participate in light recreational activities during studies (eg, watching television, reading).
2. Subjects will be asked to refrain from the following for 24 hours prior to their visits:
 - Dangerous sport activities (eg, skiing, mountain climbing, etc.)
 - Swimming in a chlorinated pool
 - Challenging climates (eg, smoking rooms, sauna, etc.)

6.4. Screen Failures

Screen failures are defined as subjects who consent to participate in the clinical study but are not subsequently entered in the study. A minimal set of screen failure information is required to ensure transparent reporting of screen failure subjects to meet the Consolidated Standards of Reporting Trials (CONSORT) publishing requirements and to respond to queries from regulatory authorities. Minimal information includes demography, screen failure details, eligibility criteria, and any serious adverse event (SAE).

Individuals who do not meet the criteria for participation in this study (screen failure) may not be rescreened.

7. Treatments

7.1. Treatments Administered

For both Part A and Part B, starting at Day -14 (Placebo Run-In), subjects will instill 1 drop of Placebo into each eye [REDACTED]

In Part A, subjects will instill 1 drop of SJP-0132 or placebo into each eye (one time only).

In Part B, subjects will instill 1 drop of SJP-0132 or placebo into each eye [REDACTED]

7.2. Investigational Product Information

The amount of SJP-0132 per mL [REDACTED]:

0.03% = 0.3 mg

0.1% = 1 mg

0.3% = 3 mg

1% = 10 mg

Non-active excipients include tyloxapol, boric acid, sodium borate, and United States Pharmacopeia (USP) purified water.

7.3. Preparation/Handling/Storage/Accountability

[REDACTED]

Doses and dosing times while at the clinic will be recorded in the subject source document.

For each instance where study drug is dispensed, site will provide subject education on self-administration, storage, and handling of study drug.

When the subjects self-medicate at home, they will record the date and time of each dose in a diary. The diary will be collected and reviewed at each clinic visit.

At each visit, the study site will remind each subject to bring study drug with them to the next visit, for study drug return and dispensing.

In the instance that a bottle of study drug is lost, the subject should contact the site immediately, and schedule to return to the site for a replacement bottle to be dispensed.

7.4. Dose Modification

Dose modification is not permitted.

7.5. Method of Treatment Assignment

Subjects will be randomly assigned to SJP-0132 or placebo using a computer-generated randomization scheme.

Part A: 4 cohorts consisting of 8 subjects each (non-Japanese), with 6 subjects randomized to SJP-0132 ophthalmic [REDACTED] and 2 randomized to placebo.

- Cohort 1: 0.03% SJP-0132 / Placebo
- Cohort 2: 0.1% SJP-0132 / Placebo
- Cohort 3: 0.3% SJP-0132 / Placebo
- Cohort 4: 1% SJP-0132 / Placebo

Part B: 2 cohorts consisting of 30 subjects each (9 Japanese and 21 non-Japanese) 20 randomized to SJP-0132 ophthalmic [REDACTED] and 10 randomized to placebo:

Cohort#	Active		Placebo		Total
	JP	Non-JP	JP	Non-JP	
5	6	14	3	7	30
6	6	14	3	7	30
Total	12	28	6	14	60

JP = Japanese

Doses selected for Part B will be determined after evaluation of safety and tolerability in Part A. The first cohort randomized in Part B (Cohort 5) will receive the second maximum acceptable concentration of SJP-0132 ophthalmic [REDACTED] or placebo [REDACTED]

[REDACTED] 4 weeks. The second cohort randomized in Part B (Cohort 6) will receive the maximum acceptable dose of SJP-0132 ophthalmic [REDACTED] or placebo [REDACTED] for 4 weeks.

7.6. Masking

Subjects will be randomly assigned to receive study treatment. Investigators will remain masked to each subject's assigned study treatment throughout the course of the study. In order to maintain this mask, an otherwise uninvolved 3rd party will be responsible for the reconstitution and dispensation of all study treatment and will endeavor to ensure that there are no differences in time taken to dispense following randomization.

This 3rd party will instruct the subject to avoid discussing the taste, color, dosing frequency, or packaging of the study treatment with the investigator.

In the event of a Quality Assurance audit, the auditor(s) will be allowed access to unmasked study treatment records at the site(s) to verify that randomization/dispensing has been done accurately.

The mask may be broken if, in the opinion of the investigator, it is in the subject's best interest for the investigator to know the study treatment assignment. The sponsor must be notified before the mask is broken unless identification of the study treatment is required for a medical emergency in which the knowledge of the specific masked study treatment will affect the immediate management of the subject's condition. In this case, the sponsor must be notified within 24 hours

after breaking the mask. The date and reason that the mask was broken must be recorded in the source documentation and CRF, as applicable.

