9.3. Adverse Events

The definitions of an AE or SAE can be found in [Appendix 4](#).

AEs will be recorded from the beginning of the run-in phase. Any medical occurrence before run-in will be recorded as medical history. AE will be reported by the subject (or, when appropriate, by a caregiver, surrogate, or the subject's legally authorized representative).

The investigator and/or designees are responsible for detecting, documenting, and recording events that meet the definition of an AE or SAE and remain responsible for following up AEs that are serious, considered related to the study treatment or study procedures, or that caused the subject to discontinue the study (see [Section 8](#)).

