9.3.2. Method of Detecting AEs and SAEs

Care will be taken not to introduce bias when detecting AEs and/or SAEs. Open-ended and non-leading verbal questioning of the subject is the preferred method to inquire about AE occurrences.

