9.4. Treatment of Overdose

An overdose occurring from topical administration of SJP-0132 ophthalmic [REDACTED] is unlikely but in the case of a suspected overdose, the subject will be instructed to contact the investigator or study coordinator immediately. General support measures should be used in the case of excessive pharmacological effects or overdose. No antidotes are available.

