Examples of such events include invasive or malignant cancers, intensive treatment in an emergency room or at home for allergic bronchospasm, blood dyscrasias or convulsions that do not result in hospitalization, or development of drug dependency or drug abuse.

Recording and AE and/or SAE

AE and SAE Recording

- When an AE/SAE occurs, it is the responsibility of the investigator to review all documentation (eg, hospital progress notes, laboratory reports, and diagnostics reports) related to the event.
- The investigator will then record all relevant AE/SAE information in the CRF (eg, event term, date and time of onset, date and time of resolution, anatomical site or system). If the AE/SAE is to an eye, the study eye or fellow eye must be identified.
- It is **not** acceptable for the investigator to send photocopies of the subject's medical records to Senju in lieu of completion of the AE/SAE CRF page.
- There may be instances when copies of medical records for certain cases are requested by Senju. In this case, all subject identifiers, with the exception of the subject number, will be redacted on the copies of the medical records before submission to Senju.
- The investigator will attempt to establish a diagnosis of the event based on signs, symptoms, and/or other clinical information. Whenever possible, the diagnosis (not the individual signs/symptoms) will be documented as the AE/SAE.

Assessment of Intensity

The investigator will make an assessment of intensity for each AE and SAE reported during the study and assign it to 1 of the following categories:

- Grade 1 (Mild): asymptomatic or mild symptoms; clinical or diagnostic observations only; intervention not indicated.

- Grade 2 (Moderate): minimal, local or non-invasive intervention indicated; limiting age appropriate instrumental ADL*.
- Grade 3 (Severe): medically significant but not immediately life-threatening; hospitalization or prolongation of hospitalization indicated; disabling; limiting self-care ADL.
- Grade 4 (Life threatening): urgent intervention indicated
- Grade 5 (Death): death related to AE

An event is defined as 'serious' when it meets at least 1 of the predefined outcomes as described in the definition of an SAE, NOT when it is rated as severe.

* Activities of daily living

Assessment of Causality

- The investigator is obligated to assess the relationship between study treatment and each occurrence of each AE/SAE.

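### Section 7.6 asks subjects not to discuss taste with the investigator and makes no exception for symptoms, so taste-related AEs may be under-reported

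*Combined protocol and SAP*

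**What the plan says.** Section 7.6 (Masking) gives the dispensing of study treatment to an otherwise uninvolved third party and adds: "This 3rd party will instruct the subject to avoid discussing the taste, color, dosing frequency, or packaging of the study treatment with the investigator". The section contains no exception for symptoms.

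AE collection rests on what the subject says. Section 9.3 states "AE will be reported by the subject", with a caregiver or representative standing in where appropriate, and "The investigator and/or designees are responsible for detecting, documenting, and recording events that meet the definition of an AE or SAE". Section 9.3.2 adds: "Open-ended and non-leading verbal questioning of the subject is the preferred method to inquire about AE occurrences". Appendix 4 counts any unfavorable and unintended symptom temporally associated with study treatment as an AE, and under its causality heading says: "The investigator is obligated to assess the relationship between study treatment and each occurrence of each AE/SAE".

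Section 4 makes the number and severity of AEs a primary endpoint. Section 5.1 lists AEs among the data reviewed before Cohort 6 may begin.

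Dosing is recorded elsewhere. Under Section 7.3, clinic doses go into the source document and home doses into a dated and timed diary: "The diary will be collected and reviewed at each clinic visit". Section 7.7 sends actual dosing times after a missed dose to the same diary. Section 9.4 says that "in the case of a suspected overdose, the subject will be instructed to contact the investigator or study coordinator immediately".

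**The concern.** Two instructions to the same subject point in different directions. One asks the subject to volunteer anything untoward. The other names taste as a topic to keep from the investigator. The masking sentence is evidently aimed at product attributes that could reveal allocation, but a subject is not well placed to separate a remark about how the product tastes from a complaint that it leaves a bad taste. Someone who follows the instruction as worded may say nothing.

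What is at stake is the completeness of one class of tolerability event in a study whose primary objectives include tolerability. If the active drops taste different from placebo, the missing reports would belong to events that differ by arm, and the tolerability comparison would lean toward no difference.

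**Working it through.** The plan states no figure on this point, so there is none to reproduce. The check is a comparison of provisions.

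1. **Can a taste complaint be an AE?** Yes. The Appendix 4 definition covers any unfavorable, unintended symptom temporally associated with treatment and is not limited to ocular symptoms.

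2. **Is there another prompt for it?** None was found.
   - The nine VAS items (Section 4) are dryness, discomfort, burning/stinging, sticky feeling, foreign body sensation, itching, pain, blurred vision and sensitivity to light.
   - OSDI and DEQ-5 are listed as dry eye symptom scores; their items are not reproduced in the protocol.
   - The added irritation assessment in Section 5.1 is ocular.
   - The physical examination in Section 9.2.2 names body systems and includes no question on taste.
   - Open questioning under Section 9.3.2 is therefore the only route described, and it depends on the subject raising the matter.

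3. **Does Section 7.6 narrow that route?** Read literally, yes. The subject is told not to raise taste with the investigator, who must also assess causality for each AE.

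4. **Could subjects notice a difference?** All subjects instill placebo from Day -14 (Section 7.1), so those later given active treatment have a reference. Whether the active drops do taste different cannot be learned from the readable text.

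5. **Direction of the bias.** Let the true proportions with a taste-related AE be p_A (active) and p_P (placebo). Assume that the same fraction k of these events is reported in both arms, since the same instruction goes to everyone. The expected observed difference is k·p_A − k·p_P = k(p_A − p_P). For k below 1 this is nearer zero than the true difference. Under a common k the ratio of the two proportions does not change in expectation, but both arms show fewer events. If p_A = p_P, no difference is distorted; events are only under-counted.

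6. **Size.** The documents give none of k, p_A or p_P. Any number would come entirely from assumed values, so none is offered.

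7. **Does the same reasoning reach dosing?** No. Each type of dosing departure has a record that does not depend on conversation with the investigator, or has an explicit instruction to make contact:
   - clinic doses: source document (Section 7.3);
   - home doses: reviewed diary (Section 7.3);
   - missed doses: actual times in the diary (Section 7.7);
   - suspected overdose: immediate contact with the investigator or coordinator (Section 9.4).

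8. **Does it reach dose selection?** Hardly. Section 5.1 defines the maximum acceptable dose by the number of subjects with a severe drug-related AE. Appendix 4 describes Grade 3 (severe) as medically significant, disabling, limiting self-care, or with hospitalization indicated. A taste complaint is unlikely to reach that grade.

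**The case against.** The strongest reply is that Section 7.6 lists product attributes as possible unmasking cues and does not tell anyone to withhold a symptom. AEs are reviewed at every visit, and designees as well as the investigator may detect and record them, so a route exists that the instruction does not close. Local tolerability is well covered by the VAS, the irritation assessment and repeated slit-lamp examinations, which leaves at most one non-ocular symptom exposed. Taste may also be the cue most likely to unmask, and central corneal staining is a co-primary efficacy endpoint, so removing the word would weaken a real safeguard.

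Much of this stands. The intent is masking, ocular tolerability is not at issue, and deleting taste from the list would be a poor remedy. The designee argument is incomplete: no text tells subjects that they may report taste to someone else, and the investigator must in any case learn of each AE in order to judge causality. Good intent does not supply the missing exception.

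A reader might go further and infer that dosing errors and overdoses are hidden as well, since dosing frequency is on the same list. The documents do not support that. The list mentions frequency, not missed or extra doses, and Sections 7.3, 7.7 and 9.4 capture these separately. Appendix 4 also does not treat an overdose in itself as an AE or SAE unless it is intentional with possible self-harm intent; the signs, symptoms and sequelae of a suspected overdose do count.

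**Conclusion.** The point holds as a wording defect limited to taste. Followed as written, Section 7.6 can lead subjects not to report an unpleasant or altered taste, and no other provision would reliably recover the event. If active and placebo taste different, and reporting is reduced to a similar degree in both arms, the observed difference in taste-related AEs is biased toward zero. The documents do not allow the size to be estimated.

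Two stronger inferences should be resisted. The under-reporting is not deliberate suppression; what is missing is an exception. Nor do the documents support a distorted choice of Part B doses, since that rule turns on severe drug-related AEs. The review before Cohort 6 does include AEs generally, but nothing in the text shows that taste reports would change its outcome.

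The conclusion rests on a literal reading by subjects and on the readable text. Redacted passages on the regimen, and subject materials outside these documents, could already contain the exception.

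**What to change.** Keep the masking sentence in Section 7.6 and add after it: 'This instruction does not restrict reporting of any symptom, including an unpleasant or altered taste, or of any missed or extra dose or suspected overdose; these should be reported to site staff and assessed under Section 9.3 and Appendix 4.' Carry the same sentence into the subject instructions. The AE definition stays as it is, so ordinary drop sensations do not automatically become AEs, and the dosing records in Sections 7.3, 7.7 and 9.4 are unchanged.

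Optionally, remove dosing frequency from the list unless redacted text shows that it differs by arm. In the readable text, Part A is a single dose for all, and the Part B dosing times of 0, 4, 8 and 12 hours are the same for active and placebo, so the item appears to add little to the mask.

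The cost is one protocol sentence and a matching edit to subject materials. The downside is that a taste report may hint at allocation to the investigator. Routing the report through other staff would not remove that risk, because the investigator still assesses causality. It is a small price for more complete recording of a primary safety endpoint.
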